4 STUDY DESIGN

4.1 Overall Design

This is a Phase 3, randomized, double-blind, active comparator-controlled clinical study to evaluate the safety, tolerability, and immunogenicity of V116 in children and adolescents aged ≥ 2 to < 18 years who have completed a primary pneumococcal vaccination regimen and who are at increased risk of pneumococcal disease (ie, chronic heart disease, chronic lung disease, diabetes mellitus, chronic liver disease, or chronic kidney disease).

Approximately 820 participants will be randomized in a 3:2 ratio to receive a single dose of either V116 or PPSV23 on Day 1. Randomization will be stratified by the number of increased-risk conditions for pneumococcal disease (1 increased-risk condition, or ≥ 2 increased-risk conditions) and by prior pneumococcal vaccination and age:

- Prior PCV7 alone
- Prior PCV7 and one prior PPSV23 dose
- Prior PCV10 alone and ≥ 2 to < 6 years old
- Prior PCV10 alone and ≥ 6 to < 18 years old
- Prior PCV10 and one prior PPSV23 dose
- Prior PCV13 alone and ≥ 2 to < 6 years old
- Prior PCV13 alone and ≥ 6 to < 18 years old
- Prior PCV13 and one prior PPSV23 dose

Note: Participants who previously received a combination of PCV7, PCV10, and/or PCV13 or any doses of PCV15 or PCV20 will be excluded from this study.

Participants are to have ≥ 1 increased-risk condition listed in Inclusion Criteria #1 (Section 5.1). It is expected that ≥ 25 participants per risk condition will be enrolled. In participants with ≥ 2 increased-risk conditions, each condition will count towards the total per condition.

Participants risk condition(s) must be considered stable for ≥ 3 months with no anticipated major change in treatment expected for the duration of the study and with ≤ 1 hospitalization directly related to the risk condition within 3 months before study vaccination.

An eVRC will be used by the participant/participant's legally authorized representative to record solicited injection-site AEs, solicited systemic AEs, and daily body temperatures from Day 1 through Day 5 after vaccination. Unsolicited AEs will also be recorded from Day 1 through Day 30 after vaccination. The participant/participant's legally authorized representative will be provided an electronic device or have their own electronic device configured, if compatible, to complete the eVRC.

Blood samples for immunogenicity assays will be drawn on Day 1 (Visit 1) and Day 30 (Visit 3).

Information for SAEs and deaths, regardless of whether the events are considered to be vaccine-related by the investigator, will be collected through completion of participation in the study.

An external DMC will conduct a periodic review of safety and tolerability data for the V116 Phase 3 program. A description of the structure and function of the DMC, along with the timing and content of the safety reviews, will be outlined in the DMC charter. Information regarding the composition of the DMC is provided in Appendix 1.

Specific procedures to be performed during the study, including prescribed times and associated visit windows, are outlined in Section 1.3 of the SoA. Details of each procedure are provided in Section 8.

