5.1 Inclusion Criteria

An individual is eligible for inclusion in the study if the individual meets all of the following criteria:

Type of Participant and Disease Characteristics

1. Documented diagnosis of ≥ 1 of the following risk conditions for pneumococcal disease as determined by the investigator, according to local clinical standards, which includes history and physical examination in combination with diagnostic tests and procedures and managed per local guidelines:
 - Diabetes mellitus receiving treatment with antidiabetic medication
 - Chronic compensated liver disease
 - Chronic lung disease, including but not limited to asthma (a diagnosis of asthma requires current medical therapy)
 - Chronic heart disease due to heart failure, congenital heart disease, cardiomyopathy, and/or valvular heart disease
 - Chronic kidney disease, with chronic kidney insufficiency/impairment
2. Receiving stable medical management for the risk conditions listed in Inclusion Criterion #1 for ≥ 3 months with no anticipated major change in treatment expected for the duration of the study and with ≤ 1 hospitalization directly related to the risk condition within 3 months before study vaccination.
3. At least 8 weeks prior to enrollment, completed primary PCV regimen with PCV7, PCV10, or PCV13 with either a 2+1 or 3+1 regimen according to local recommendations; all doses of the primary regimen must be of the same vaccine.
 - a. 2+1: 2 priming doses followed by 1 booster dose administered prior to 2 years of age
or
 - b. 3+1: 3 priming doses followed by 1 booster dose administered prior to 2 years of age

4. Is PPSV23 vaccine-naïve (participant who has never received PPSV23), or PPSV23 vaccine-experienced (participant who has received not more than 1 dose of PPSV23) ≥ 5 years before study vaccination.

Demographics

5. Is an individual of any sex/gender, from ≥ 2 years to < 18 years of age, at the time of providing the informed consent/assent.

Assigned Female Sex at Birth

6. A participant assigned female sex at birth is eligible to participate if not pregnant or breastfeeding, and at least one of the following conditions applies:
 - Is not a POCBP
OR
 - Is a POCBP and:

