5.2 Exclusion Criteria

An individual must be excluded from the study if the individual meets any of the following criteria:

Medical Conditions

1. Had a curative procedure/surgery for chronic heart disease and does not require medication, follow-up, additional interventions, or further management per local guidelines.
2. Has a history of active hepatitis within 3 months before study vaccination (Day 1).
3. Has a history of diabetic ketoacidosis or 2 or more episodes of severe, symptomatic hypoglycemia within 3 months before study vaccination (Day 1).
4. Has a history of severely decreased kidney function (outlined in the Investigator Trial File Binder for this study), dialysis, autoimmune related chronic kidney disease, nephrotic syndrome of any cause, or an acute/reversible cause of kidney disease.
5. Has a history of severe pulmonary hypertension or history of Eisenmenger syndrome.
6. Has a history of IPD (positive blood culture, positive cerebrospinal fluid culture, or positive culture at another sterile site) or known history of other culture-positive pneumococcal disease within 3 years before study vaccination (Day 1).
7. Has a known hypersensitivity to any component of PPSV23 or V116 (including diphtheria toxoid).
8. Has a known or suspected impairment of immunological function including, but not limited to, congenital or acquired immunodeficiency, documented HIV infection, functional or anatomic asplenia, or autoimmune disease (including, but not limited to, the autoimmune conditions outlined in the Investigator Trial File Binder for this study).
9. Has a coagulation disorder contraindicating intramuscular vaccination.
10. *Had a recent febrile illness (defined as temperature $\geq 100.4^{\circ}\text{F}$ [$\geq 38.0^{\circ}\text{C}$]) or received antibiotic therapy for any illness occurring within 72 hours before receipt of study vaccine.
11. Has a known malignancy that is progressing or has required active treatment < 3 years before randomization. **Note:** Participants with basal cell and/or squamous cell carcinoma of the skin, or carcinoma in situ that have undergone potentially curative therapy, are not excluded.
12. Planned organ transplantation (heart, liver, lung, kidney, or pancreas) or other planned major surgical procedure during the duration of this study.

13. Expected survival for <1 year according to the investigator's judgment.

Prior/Concomitant Therapy

14. Received ≥ 1 dose of PCV15 or PCV20.

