15. Is expected to receive any pneumococcal vaccine during the study outside of the protocol.

16. *Received or is scheduled to receive systemic corticosteroids (total daily dose prednisone equivalent of ≥ 2 mg/kg or ≥ 20 mg/day for children > 10 kg) for ≥ 14 consecutive days and has not completed intervention ≥ 14 days before receipt of study vaccine (Day 1) and through 30 days following vaccination. **Note:** Physiologic replacement doses (prednisone equivalent of approximately 5 mg/day), topical, ophthalmic, intraarticular or soft-tissue (eg, bursa, tendon steroid injections), and inhaled/nebulized steroids are permitted.

17. Is currently receiving systemic immunosuppressive therapy, including chemotherapeutic agents or other immunotherapies/immunomodulators used to treat cancer or other conditions, and interventions associated with organ or bone marrow transplantation, or autoimmune disease.

18. *Received any nonlive vaccine ≤ 14 days before receipt of study vaccine or is scheduled to receive any nonlive vaccine ≤ 30 days after receipt of study vaccine. Exception: Inactivated influenza vaccine and SARS-CoV-2 mRNA or SARS-CoV-2 protein subunit vaccine may be administered but must be given ≥ 7 days before or ≥ 15 days after receipt of study vaccine.

19. *Received any live virus vaccine (including SARS-CoV-2 live virus vaccines) ≤ 30 days before receipt of study vaccine or is scheduled to receive any live virus vaccine ≤ 30 days after receipt of study vaccine.

20. Received a blood transfusion or blood products, including immunoglobulin ≤ 6 months before receipt of study vaccine or is scheduled to receive a blood transfusion or blood product ≤ 30 days after receipt of study vaccine. Autologous blood transfusions are not considered an exclusion criterion.

21. Receiving chronic home oxygen therapy.

Prior/Concurrent Clinical Study Experience

22. Is currently participating in or has participated in an interventional clinical study with an investigational compound or device within 2 months of participating in this current study.

Diagnostic Assessments

Not Applicable.

Other Exclusions

23. In the opinion of the investigator, has a history of clinically relevant drug or alcohol use that may interfere with participation in protocol-specified activities.

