24. Has history or current evidence of any condition, therapy, laboratory abnormality, or other circumstance that might expose the participant to risk by participating in the study, confound the results of the study, or interfere with the participant's participation for the full duration of the study.
25. Has a parent/legal guardian/legally acceptable representative who is unlikely to adhere to study procedures, keep appointments, or is planning to relocate during the study.
26. Is or has an immediate family member (eg, spouse, parent/legal guardian, sibling, or child) who is investigational site or Sponsor staff directly involved with this study.

For Exclusion Criteria with an asterisk (*), if the participant meets these exclusion criteria, Visit 1 may be rescheduled for a time when these criteria are not met.

Country-specific criteria are included in Appendix 7.

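### Does the Section 4.1 note on mixed prior PCVs contradict the numbered eligibility criteria in Section 5?

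*Combined protocol and SAP*

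**What the plan says.** Protocol Section 4.1 lists the randomization strata for prior pneumococcal vaccination and age, then adds a note: "Participants who previously received a combination of PCV7, PCV10, and/or PCV13 or any doses of PCV15 or PCV20 will be excluded from this study".

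Section 5.1 opens its list with "An individual is eligible for inclusion in the study if the individual meets all of the following criteria". Four of the numbered criteria deal with receipt of a pneumococcal vaccine:

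- Inclusion 3 asks for a completed 2+1 or 3+1 primary series of PCV7, PCV10 or PCV13, with the booster before age 2, and says "all doses of the primary regimen must be of the same vaccine".
- Inclusion 4 admits PPSV23-naïve children, or a "participant who has received not more than 1 dose of PPSV23", given at least 5 years before study vaccination.
- Exclusion 14 bars anyone with at least one "dose of PCV15 or PCV20".
- Exclusion 15 looks forward only: "Is expected to receive any pneumococcal vaccine during the study outside of the protocol".

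Two general criteria could also reach an earlier PCV dose. Exclusion 18 ("Received any nonlive vaccine") applies within 14 days before study vaccine, or 15 days at EEA sites, and Visit 1 may be rescheduled. Exclusion 24 begins "Has history or current evidence of any condition, therapy, laboratory abnormality, or other circumstance" and extends to anything that might confound the results.

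Section 8.11.1 directs screening to Section 5. Section 4.2 explains that stratification follows the PCV regimen given in infancy and any prior PPSV23, because earlier pneumococcal vaccination may affect responses to the shared serotypes.

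**The concern.** The note in 4.1 has two halves. The PCV15/PCV20 half reappears in full as Exclusion 14. The half on mixing PCV7, PCV10 and PCV13 reappears only as a rule about the primary series. The note itself sets no such limit, so a child who finished a PCV10 series in infancy and later had PCV13 seems to be barred by 4.1 while passing every numbered criterion that names a pneumococcal vaccine.

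The history is conceivable. Section 2.2.2.2 mentions PCV13 among the vaccines that EU guidelines recommend for at-risk children after the primary regimen.

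If the two sections did disagree, sites could screen the same child differently, the enrolled population would be less sharply defined, and the child's randomization stratum would be unclear. Because Section 4.2 expects prior vaccination to matter for the shared serotypes, this looks more than cosmetic at first.

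**Working it through.** The plan states no figure on this point, so the check is a comparison of text. Section 5.1 has 7 criteria and Section 5.2 has 26, so 7 + 26 = 33. Those on receipt of a pneumococcal vaccine are Inclusion 3, Inclusion 4, Exclusion 14 and Exclusion 15, which makes 4. Of these, 0 name a later dose of a different PCV7, PCV10 or PCV13.

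**Test child.** PCV10 2+1 completed before age 2, one PCV13 dose later (well outside the Exclusion 18 window), no PPSV23.

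| Place | Result for this child |
|---|---|
| 4.1 note, read as any time | Excluded |
| 4.1 note, read as the infancy regimen | Not excluded |
| Inclusion 3 | Met: the primary doses are one product |
| Inclusion 4 | Met: PPSV23-naïve |
| Exclusions 14 and 15 | Not triggered |
| Exclusion 18 | Not triggered |
| Exclusion 24 | Triggered if the history might confound the results |
| Strata in 6.3.2 | Neither PCV10 alone nor PCV13 alone fits on plain wording |
| Appendix 7 | Replaces Exclusion 18 (Japan) and Exclusions 17 and 18 (EEA); nothing on PCV history |

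**Is there a contradiction?** That would need one passage to bar the child and another to admit the child. The opening sentence of 5.1 governs only the inclusion list; meeting it does not secure entry, because 5.2 adds exclusions. Nothing in Section 5 says a mixed PCV history is acceptable. On the broad reading, 4.1 supplies a further mandatory exclusion, and Section 8 makes adherence to the study design a requirement. On the narrow reading, 4.1 and Inclusion 3 state the same rule. Each reading gives one answer once the protocol is read as a whole.

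**Which reading is natural?** The note stands directly beneath the strata, and Section 4.2 says those strata reflect the infancy regimen. That favors the narrow reading but does not prove it, since the note lacks the limiting words. On the broad reading two other features point the same way as the note. Exclusion 24 is mandatory: unlike Exclusion 23, it is not worded as a matter of the investigator's opinion, although applying it takes judgment. And the strata offer a mixed history no clear place.

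**What if such a child is enrolled?**

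1. Eligibility and stratum are fixed before allocation, so the V116 versus PPSV23 comparison stays randomized. No bias arises.
2. The power statement in 9.8.1 rests on GMT ratios and standard deviations from V116-004 and on 90% evaluability (0.90 × 492 = 442.8, given as 443; 0.90 × 328 = 295.2, given as 295). The eligibility wording enters none of these inputs.
3. Each serotype is tested at one-sided 0.025 under 9.7. The wording does not affect this.
4. Section 8.1.5.1 records any earlier pneumococcal vaccination regardless of date, so the child can be identified. Section 9.4.1 settles the per-protocol population before unblinding and adds a supportive FAS analysis, so any decision about such a child would be taken blind to assignment.

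**The case for a change.** The strongest case for a change is practical. Screeners are sent to Section 5, not 4.1, and Section 5 forbids waivers of enrollment criteria, so those criteria ought to be complete. One half of the note was carried over in full and the other was not, which suggests an oversight. Sections 6.5 and 9.4.1 refer to prohibited vaccines, and an earlier dose of a different PCV is not named as prohibited in 5.2, so the child's per-protocol status is also not spelled out. Exclusion 24 names no PCV history, and sites could apply it differently. *Alone* in the strata may mean only without PPSV23, in which case the strata are no barrier. The repair would be a line of text and would need no new data.

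Part of this stands. The carry-over is incomplete if the broad reading is meant, and 8.11.1 does point only to Section 5. The per-protocol point is weaker, because the list in 9.4.1 is of potential deviations and is not presented as closed.

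What is missing is a consequence. The repair would record which reading the sponsor intends, and no analysis or conclusion changes under either. The extent is also unknown. Section 2.2.2.2 does not say that PCV13 follows a different primary product, and PCV13 after a PCV13 series is not a combination. The same section calls a single PPSV23 dose the most widely recommended regimen. A child who had both a later PCV13 dose and PPSV23 would also have to meet the 5-year gap in Inclusion 4.

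**Conclusion.** The difference in wording is real, but it is a minor editorial gap and calls for no change. Section 4.1 leaves open whether mixing concerns the infancy series or any time, and Section 5 states only the former. Read with Section 4.2 the two agree. Read broadly, 4.1 adds an exclusion that nothing in Section 5 overrides.

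Its size is 1 of the 2 halves of one note, carried into Section 5 for the primary regimen only. No effect on bias, power, type I error or the trial's conclusions is shown.

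This rests on two things. The first is that enrollment decisions are made before allocation, as the protocol provides. The second is that vaccination histories are recorded as 8.1.5.1 requires, so that any ambiguous case is visible before unblinding. The number of such children cannot be derived from the documents. The absence of bias does not depend on it.

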4.2 Scientific Rationale for Study Design

This study will evaluate the safety, tolerability, and immunogenicity of V116 in children and adolescents ≥ 2 to < 18 years of age who have completed a primary pneumococcal vaccination regimen and who are at increased risk for pneumococcal disease.

Children and adolescents with one or more stable chronic medical conditions, including chronic heart disease, chronic lung disease, diabetes mellitus, chronic liver disease, and chronic kidney disease will be included in this study. The population of children and adolescents with these chronic medical conditions are at increased risk for IPD and were selected for inclusion based on their overall prevalence in the pediatric population (Section 2.1).

The randomization ratio of 3:2 was chosen to increase the number of participants exposed to V116 to expand the V116 safety and immunogenicity data in a population at increased risk for pneumococcal disease.

Participants will be stratified by prior PCV regimen received in infancy and prior PPSV23 vaccination, as prior pneumococcal vaccination may impact immune responses to V116 and PPSV23 for the shared serotypes. Participants will also be stratified by the number of risk conditions (1 increased-risk condition only or ≥ 2 increased-risk conditions) as it is expected that the number of participants enrolled with 1 or more conditions will vary and to ensure balance between the intervention groups. Participants will also be stratified by age (≥ 2 to < 6 and ≥ 6 to < 18 years of age) for those who received PCV10 and PCV13 alone to ensure balance between the intervention groups.

Individuals with severe heart, liver, lung, or kidney disease, and those with uncontrolled diabetes will be excluded from this study to allow them to prioritize their medical care over participation in this study and to avoid associating the effects of medical treatment with the safety and immunogenicity of the vaccine.

4.2.1 Rationale for Endpoints

4.2.1.1 Safety Endpoints

Safety information will be collected from all participants (or participant's legally acceptable representative) on an eVRC. The eVRC used to record AEs during the postvaccination period(s) (Section 8.1.10) is structured as recommended in the final US FDA Patient-reported Outcome Guidance [U.S. Food and Drug Administration 2009].

The safety endpoints (ie, AEs and temperature) evaluated in this study are consistent with previous studies of V116 and published data from marketed PCVs. Detailed information for the safety endpoints evaluated in this study can be found in Section 9.3.2.

Definitions and reporting requirements for AEs are provided in Appendix 3.

4.2.1.2 Immunogenicity Endpoints

The immunogenicity endpoints are consistent with previous studies evaluating PCVs.

According to the CHMP and WHO guidance documents, immunogenicity studies can be conducted to support the licensing of new pneumococcal vaccines [European Medicines Agency 2006] [World Health Organization 2016] [World Health Organization 2013]. The OPA GMT, IgG GMC, GMFR, and proportion of participants with a 4-fold rise in OPA and IgG responses are acceptable assessments used to evaluate novel PCVs. Several studies have shown a positive correlation between serotype-specific OPA titers and IgG antibody concentrations in children and adults [Centers for Disease Control and Prevention 2010] [Anttila, M., et al 1999] [Romero-Steiner, S., et al 1997].

Thresholds of protection have been established in children <2 years of age, where serotype-specific IgG of ≥ 0.35 $\mu\text{g/mL}$ measured by ELISA one month after primary immunization was used for the licensing of PCV based on analyses of pooled immunogenicity and efficacy data from randomized controlled studies of the initial 7-valent and investigational 9-valent PCVs [World Health Organization 2013]. However, this threshold is not as relevant for older children, especially those who have already completed a primary pneumococcal vaccination regimen. OPA titers provide an assessment of functional immune responses as a surrogate marker for vaccine efficacy against pneumococcal disease and have been shown to correlate with vaccine-induced protection. Based on this, OPA titers will be used as the primary immunogenicity endpoint in this study. It is noted that OPA titer threshold values that correlate with protection in any age group have not been defined.

Sera from participants will be used to assess vaccine-induced, anti-PnPs, serotype-specific OPA and IgG responses using the validated MOPA and Pn ECL assay, respectively. Immunogenicity endpoints will be evaluated for all serotypes included in V116 and for cross-reactive serotypes within a serogroup.

Details on the immunogenicity endpoints evaluated in this study can be found in Section 9.3.1.

